#### **12.2.4 Analysis of other tolerability and safety variables**

Adverse events will be coded for analysis with the latest version of the Medical Dictionary for Regulatory Activities (MedDRA®).

An ADR is a response to a prescribed treatment that is noxious and not intended. Response in this context means that a causal relationship between a medicinal product and an AE is at least a reasonable possibility.

Time to discontinuation of BRV due to ADRs, from the date of first dose of BRV, will be analyzed using Kaplan-Meier methods. The median time to discontinuation (days) of BRV will be presented along with the 25% and 75% quartiles.

For each of the following event types, frequency tables with the number of events, the number of patients who experience the event, and the percentage of patients who experience the event will be presented by MedDRA system organ class and preferred term:

- Treatment-emergent AEs and ADRs
- Treatment-emergent AEs and ADRs with an incidence  $\geq 5\%$
- Serious treatment-emergent AEs and ADRs
- ADRs leading to permanent discontinuation of BRV

These analyses will be performed on the SS and may be repeated on the modified FAS.

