#### 8.1.2 Sensitivity analysis of the primary variable retention at 12 months

The 12 month retention analysis described in [Section 8.1.1](#) will be repeated on the modified FAS as a sensitivity analysis to represent the retention of patients who take BRV per the SmPC.

In addition, a Kaplan-Meier analysis of time to discontinuation of BRV or study termination will be provided on the FAS and the modified FAS. Time to discontinuation of BRV or study termination will be calculated as:

Minimum of (Date of last administration of BRV while in the study, Date of study termination) – date of first BRV administration + 1

A patient will be considered as having an event if the patient discontinues from the study (Study Termination [Dropout] CRF page completed) or if the patient is not prescribed Brivaracetam

after exiting the study (ie, answer to the CRF question “Will the subject be prescribed Brivaracetam after exiting the EP0077 study?” is “No”). All other patients will be considered as not having an event and will be censored at the date of study termination. For snapshot analyses, patients ongoing in the study will be censored at the date of data cut off.

The median time to event (days) will be presented along with the 25% and 75% quartiles and 95% CIs. In addition, the cumulative number of events, number at risk and survival estimate at monthly intervals will be provided. The Kaplan-Meier plot and raw statistical procedure output will be produced for the Kaplan-Meier analysis.

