## 10.2 Adverse events

Adverse events and other safety relevant (OSR) information such as overdose or off label use, will be recorded using UCBs Pharmacovigilance database.

The UCB SafetyAdHoc Team will provide an ad hoc listing of the safety data with an additional variable named “Case Classification (All)” that allows identification of the “non-reportable” events. Only events that are identified as “reportable” (ie, where Case Classification (All) variable does not include “Non-Reportable”) will be imported into the clinical database (SDTM). A list of MedDRA preferred terms (PTs) will be reviewed prior to database lock and used to identify OSR information. All PTs will be classified as AEs or OSR information. OSR information will not be included in the AE tables and listings, with the exception of the overview table for treatment-emergent adverse events (TEAE, see definition below) and OSR information, and the listing of AEs and OSR information that could not be reconciled.

A treatment-emergent adverse event (TEAE) is defined as an AE occurring on or after the date of first BRV administration.

An ADR is defined as a TEAE with an “as reported causality” as “related”, “unavailable” or missing.

In order to investigate the time to discontinuation of BRV due to ADRs, the time to discontinuation of BRV for all patients, will be calculated as:

Date of last administration of BRV while in the study – date of first BRV administration + 1

The date of last administration of BRV while in the study (both for completers and dropouts) and the date of first BRV administration will be taken from the CRF Study Termination (Completed Subject), Study Termination (Dropout), and First Administration of Drug pages. All patients who have an ADR with action=“Drug withdrawn” (recorded in the UCBs Pharmacovigilance

database) will be classed as having an event (discontinued BRV due to an ADR). All other patients will be censored. Time to discontinuation of BRV due to ADRs will be analyzed on the SS using Kaplan-Meier methods. The median time to discontinuation (days) of BRV due to ADRs (and 95% CI) will be presented along with the 25% and 75% quartiles (and 95% CI for the quartiles). The Kaplan-Meier plot and raw statistical procedure output will also be produced for the Kaplan-Meier analysis.

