For each of the following event types, frequency tables of incidence based on the SS will be presented. The overview analysis of TEAEs and ADRs will also be repeated on the modified FAS:

- Overview of TEAEs and OSR information (including categories for any TEAE, serious TEAE, patient discontinuations of BRV due to TEAE [derived as any TEAEs with action= “Drug withdrawn”], drug-related TEAE [ADRs], all deaths [AEs leading to death], and OSR information
- Overview of ADRs (including categories for any ADR, serious ADR, patient discontinuations of BRV due to ADRs [derived as any ADRs with action= “Drug withdrawn”], and all deaths [ADRs leading to death])
- TEAEs by MedDRA SOC and PT
- ADRs by MedDRA SOC and PT
- Non-serious TEAEs above reporting threshold of 5% of patients by MedDRA SOC and PT
- Non-serious ADRs above reporting threshold of 5% of patients by MedDRA SOC and PT
- TEAEs occurring in at least 5% of patients by MedDRA SOC and PT
- ADRs occurring in at least 5% of patients by MedDRA SOC and PT
- Serious TEAEs by MedDRA SOC and PT
- Serious ADRs by MedDRA SOC and PT
- Serious TEAEs – patient numbers
- Serious ADRs – patient numbers
- ADRs leading to permanent discontinuation of BRV by MedDRA SOC and PT
- TEAEs leading to death by MedDRA SOC and PT
- ADRs leading to death by MedDRA SOC and PT
- TEAEs by maximum relationship by SOC and PT

An AE Glossary (including the SOC, PT and reported term) will be provided separately for AEs and OSR information. In addition, the following by-patient listings for the All Subjects Documented set will be presented including the MedDRA SOC and PT, reported term, onset and outcome date, duration, seriousness, death, congenital defect, disability, hospitalization, life threatening, medically important event, outcome, relationship to study medication, and action taken with regards to study medication:

- All AEs (this listing will be repeated for patients aged <18 years only)

- All serious AEs
- All AEs leading to permanent discontinuation of BRV
- All deaths (AEs leading to death)
- OSR information
- AEs and OSR information that could not be reconciled (ie, AEs/OSR information for patient numbers that do not exist in the clinical database). This would be an ad hoc listing which will not be produced until after database lock if necessary.

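### Time to BRV discontinuation due to ADRs: Kaplan-Meier censors competing stops, so 1-KM is biased upward as a risk, and no fixed-time estimate is specified

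*SAP*

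**What the plan says.** Protocol section 12.2.4 sets the method: "Time to discontinuation of BRV due to ADRs, from the date of first dose of BRV, will be analyzed using Kaplan-Meier methods", with the median and quartiles as summaries. SAP section 10.2 follows it. Time runs from first to last BRV administration for every patient. An event is an ADR whose recorded action is withdrawal of the drug, and "All other patients will be censored". The SAP names the analysis set and estimator ("Time to discontinuation of BRV due to ADRs will be analyzed on the SS using Kaplan-Meier methods") and the summaries: "The median time to discontinuation (days) of BRV due to ADRs (and 95% CI) will be presented along with the 25% and 75% quartiles", also with CIs. It adds that "The Kaplan-Meier plot and raw statistical procedure output will also be produced for the Kaplan-Meier analysis". No competing-risk method is named anywhere.

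Three other provisions bear on the point:

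- Protocol section 8.2 withdraws a patient from the study once the physician permanently stops BRV.
- SAP section 8.1.2 promises, for the Kaplan-Meier analysis of retention, that "the cumulative number of events, number at risk and survival estimate at monthly intervals will be provided". Section 8.2.3 makes the same provision for time to first seizure. Section 10.2 has no such sentence.
- SAP section 10.2 also plans Safety Set frequency tables, including "ADRs leading to permanent discontinuation of BRV by MedDRA SOC and PT" and an ADR overview that counts patients who discontinued BRV because of an ADR.

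**The concern.** Kaplan-Meier treats a censored patient as someone who could still have the event later. That holds for a patient who leaves observation while still taking BRV. It does not hold for a patient who has stopped BRV for lack of effect, or who has died: that patient cannot afterwards stop BRV for an ADR. If these exits are censored, 1-KM estimates the risk in a setting where nobody stops BRV for any other reason. This study is meant to describe daily clinical practice, where such stops are part of what is observed.

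The second difficulty is the choice of summaries. Quartiles of time to event need the curve to fall to 75%, 50% and 25%. With observation of about a year and only one cause of stopping counted as an event, most of these levels may never be reached. The quantity a reader wants, the share who have stopped for an ADR by a given month, is not a specified output.

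**Working it through.** **Inputs.** The plan gives no figure for ADR discontinuation, so there is nothing of its own to reproduce for this analysis. The nearest figure is the expected retention of 0.50 in SAP section 2.4. Its arithmetic reproduces: (1.96/0.05)² × 0.25 = 384.1, hence 385. That 0.50 is a planning value for CI width, not a forecast. The 12-month non-retention defined in SAP section 8.1.1 also includes study termination, so it is not the same as stopping BRV. I therefore vary two assumed quantities:

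- R, the proportion still on BRV at 12 months: 0.50 to 0.80.
- s, the share of BRV stops that are due to ADRs: 0.1 to 0.7.

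**Formulas.** With proportional cause-specific hazards, the cumulative incidence of ADR discontinuation is s(1 - R). Kaplan-Meier with the other stops censored gives 1 - R^s.

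**Bias at 12 months.**

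| R | s | s(1 - R) | 1 - R^s | Excess (points) |
|---|---|---|---|---|
| 0.50 | 0.1 | 5.0% | 6.7% | 1.7 |
| 0.50 | 0.3 | 15.0% | 18.8% | 3.8 |
| 0.50 | 0.5 | 25.0% | 29.3% | 4.3 |
| 0.50 | 0.7 | 35.0% | 38.4% | 3.4 |
| 0.70 | 0.1 | 3.0% | 3.5% | 0.5 |
| 0.70 | 0.3 | 9.0% | 10.1% | 1.1 |
| 0.70 | 0.5 | 15.0% | 16.3% | 1.3 |
| 0.80 | 0.3 | 6.0% | 6.5% | 0.5 |
| 0.80 | 0.5 | 10.0% | 10.6% | 0.6 |

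At R = 0.50 the relative excess runs from about 34% (s = 0.1) down to 10% (s = 0.7).

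**Timing.** Proportional hazards is an assumption. Take R = 0.50 and a true incidence of 10%. If every ADR stop comes before any other stop, 1-KM is 10% and there is no bias. If the other 40% of patients stop first, 1-KM is 0.10/0.60 = 16.7%, an excess of 6.7 points.

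**Which quartiles are reached.** The 25% quartile needs R^s ≤ 0.75, that is s ≥ ln(0.75)/ln(R).

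| R | Smallest s | True incidence s(1 - R) at that point |
|---|---|---|
| 0.50 | 0.415 | 20.8% |
| 0.60 | 0.563 | 22.5% |
| 0.70 | 0.807 | 24.2% |
| 0.80 | 1.289 | not possible |

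The median needs R^s ≤ 0.50. At R = 0.50 that means s = 1 (every stop is an ADR stop), and at higher R it cannot happen. The 75% quartile needs R^s ≤ 0.25, which gives s = 2 at R = 0.50, so it is not possible.

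**Simulation check.** 477 patients (530 × 0.9) left between day 330 and day 400, with 2,000 runs per scenario. At R = 0.50 the 25% quartile was reached in 0.4%, 5%, 64% and 99% of runs for s = 0.2, 0.3, 0.4 and 0.5. The 64% at s = 0.4, where 1-KM is 24.2% at 12 months, reflects follow-up beyond day 365 and chance variation. The median was reached in fewer than 1% of runs in every scenario.

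**The case against.** The SAP does what the protocol prescribes. The variable is descriptive, one of the other tolerability and safety variables, in a single-group study with no inferential analyses. The real-world share who stop for an ADR is already covered by the incidence tables in section 10.2. Nothing in that section says that 1-KM will be reported as that share, and a Kaplan-Meier estimate that differs from a crude proportion is not in itself an error. The bias could also be negligible. Patients who leave the study while still on BRV are properly censored and reduce the competing fraction. The protocol's background section reports low discontinuation for AEs in the earlier trials, though without a number.

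Most of this stands, and it limits the size and priority of the point. It does not remove it. The listed variable is time to ADR discontinuation, and the crude tables have no time dimension. They also keep patients who left early on BRV in the denominator as non-events. The Kaplan-Meier plot will be read as a risk curve, and the SAP gives no warning against that reading.

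Three stronger readings are tempting, and the documents support none of them:

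- *That the analysis yields no estimable number.* A plot and raw procedure output are planned, and the raw output would normally contain the survival estimates. The 25% quartile may also be reached.
- *That the 25% quartile cannot be reached unless 25% of patients stop for ADRs.* It depends on 1-KM, which exceeds the true incidence; about 21% is enough at 50% retention.
- *That the plan as a whole overstates ADR discontinuation.* Only the Kaplan-Meier estimate does.

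**Conclusion.** The point holds as a limited one. Stops of BRV for other reasons are competing events that section 10.2 censors, so 1-KM is biased upward as the probability of stopping for an ADR. Over the assumed 10% to 70% ADR share and under proportional hazards, the excess is about 2 to 4 points at 50% retention on BRV, 0.5 to 1.3 at 70%, and no more than about 0.6 at 80%. Other timing patterns can make it zero or larger. The true size cannot be fixed, because the documents give neither the ADR share nor the rate of stopping BRV.

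The median and 75% quartile will very probably be reported as not reached. Whether the 25% quartile is reached depends on an ADR rate that is not known. The lack of specified fixed-time estimates is a plain gap beside sections 8.1.2 and 8.2.3. This is a worthwhile improvement to a descriptive safety variable and does not touch the primary analysis.

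**What to change.** Add to SAP section 10.2 the Aalen-Johansen cumulative incidence of BRV discontinuation due to ADRs on the Safety Set, at 3, 6 and 12 months with 95% CIs. Define three outcomes:

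- event: an ADR with the drug withdrawn, as now;
- competing event: BRV discontinuation for any other reason, or death;
- censored: patients who leave observation while still on BRV.

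Keep the protocol's Kaplan-Meier plot, median and quartiles as supplementary output, and state that 1-KM is not the share of patients who stop for an ADR. Record the addition in SAP section 3.9.

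No new data are needed. Protocol Table 17-1 collects the reason for BRV discontinuation, SAP section 5.1 tabulates it, and section 8.1.2 already uses the CRF question on continued prescription at study exit. The cost is SAP wording, one extra table or figure from standard software, and a small departure from the protocol's Kaplan-Meier-only wording.

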### **10.3 Clinical laboratory evaluations**

This section is not applicable as laboratory assessments are not recorded in this NIS study.

### **10.4 Vital signs, physical findings, and other observations related to safety**

This section is not applicable as vital signs and physical findings are not recorded in this NIS study.

REDACTED COPY  
This document cannot be used to support any marketing authorization application and any extensions or variations thereof

---

### 12.3 Defined Daily Dose (DDD)

Defined daily dose is the assumed average maintenance dose per day for a drug used for its main indication in adults. AEDs recorded on the study will have their DDD identified using their WHODD preferred term and the following website: [http://www.whocc.no/atc\\_ddd\\_index/](http://www.whocc.no/atc_ddd_index/)

Examples of common AEDs are provided in **Error! Reference source not found.** Whilst these can be used as a guide all medications (these and any others recorded in the CRF) should be rechecked on the website and the appropriate DDD documented in the ADAM specifications.

WHODD Preferred Term	WHO DDD (mg/day)
Acetazolamide	750
Brivaracetam	100
Carbamazepine	1000
Clobazam	20
Clonazepam	8
Clorazepate Dipotassium	20
Eslicarbazepine	800
Eslicarbazepine Acetate	800
Ethosuximide	1250
Felbamate	2400
Gabapentin	1800
Lacosamide	300
Lamotrigine	300
Levetiracetam	1500
Lorazepam	2.5
Mesuximide	900
Midazolam	15

**Table 12–1: Defined Daily Doses for common AEDs**

WHODD Preferred Term	WHO DDD (mg/day)
Midazolam Hydrochloride	15
Nitrazepam	5
Oxcarbazepine	1000
Perampanel	8
Phenobarbital	100
Phenytoin	300
Pregabalin	300
Primidone	1250
Stiripentol	1000
Sultiame	400
Tiagabine	30
Topiramate	300
Valproate	1500
Zonisamide	200

This document cannot be used to support any marketing authorization application and any extensions or variations thereof

---

## 13 AMENDMENT(S) TO THE STATISTICAL ANALYSIS PLAN (SAP)

### 13.1 AMENDMENT 1

#### Rationale for the amendment

The SAP has been amended to implement any changes to the planned analyses made during the course of the study since the approval of the previous version of the SAP and to incorporate any clarifications to the text.

#### Modifications and changes

##### Global changes

The following global changes were applied to this SAP:

- Other safety relevant (OSR) added to abbreviations.
- MedDRA version updated to be September 2015
- Descriptions of definitions required for the interim snapshot reporting.
- Seizure freedom definitions updated in section 8.2.2
- Time to first seizure definition updated and table for its derivation added to section 8.2.3
- PRN added to the list of daily dose calculations in table 8-4.
- Adverse event definition expanded upon.
- Derivation of OSR events clarified
- ADR definition expanded upon
- Classification of patients with AEs split further.
- Overview of adverse events summary rewritten.
- Flags for OSR events added to listing of AEs

## Specific changes

### Change #1

#### List of abbreviations.

The following abbreviation was added

OSR	other safety relevant
-----	-----------------------

### Change #2

#### 3.2.3 Date of last administration of BRV

If the date is missing, then use the last end date from the BRV Medication CRF page (applying the imputation of partial end dates rules as required). If that date is also missing then use the date of first BRV administration as collected on the First Administration of Drug CRF page. If this start date is partial, use a day of 01 if month and year are present, or 01 January if only year is present. If all of the above are missing, then it is assumed the patient did not take BRV.

#### Has been changed to:

For the snapshot analyses described in section 4.3, patients ongoing in the study will not yet have a date of last administration of BRV recorded. For these patients the date of last administration of BRV will be imputed using the date of the data cut off so that an estimate of the exposure to date can be calculated.

For patients who have completed or withdrawn from the study, if the date of last administration is missing, then the last end date from the BRV Medication CRF page (applying the imputation of partial end dates rules as required) will be used. If that date is also missing then the date of first BRV administration as collected on the First Administration of Drug CRF page will be used. If this start date is partial, use a day of 01 if month and year are present, or 01 January if only year is present. If all of the above are missing, then it is assumed the patient did not take BRV.

### Change #3

#### 3.8 Coding dictionaries

Medications will be coded using the March 2016 version of World Health Organization Drug Dictionary (WHODD).

#### Has been changed to:

Medications will be coded using the September 2015 version of World Health Organization Drug Dictionary (WHODD).

### Change #4

#### 4.3 Interim analyses and monitoring

- A first snapshot analysis is to be performed with a data cut-off date approximately at the end of 2016 or when 80 patients have completed Visit 2 (Month 3), whichever occurs first. All patients with available data in the database will be included in the analyses.

- A second snapshot analysis is to be performed with a data cut-off date approximately at the end of 2017, depending on recruitment status.

All planned TFLs identified in the SAP and Mock TFL shells will be delivered for the snapshot analyses including all visits in the database at time of the snapshot cut off. As data is entered in an ongoing way throughout the study, any data entered after the data cleaning cut off (but prior to the data extract) for each snapshot may not be clean. Any data discrepancies observed will be discussed and their impact on the analysis documented.

**Has been changed to:**

- A first snapshot analysis is to be performed with a data cut-off date approximately at the end of 2016 or when 80 patients have completed Visit 2 (Month 3), whichever occurs first. All patients with available data in the database will be included in the analyses. A subset of the end of study TFLs will be produced.
- A second snapshot analysis is to be performed with a data cut-off date approximately at the end of 2017, depending on recruitment status. If the recruitment schedule results in there not being enough additional data from the previous snapshot then the snapshot cut-off date may be delayed to ensure approximately 200 patients with Visit 2 (Month 3). It is expected that all TFLs identified in the SAP and Mock TFL shells will be delivered including all visits in the database at the time of the snapshot cut off.

As data is entered in an ongoing way throughout the study and cleaning is ongoing, data discrepancies in the snapshot analyses are possible. Any data discrepancies observed in the database at the time of the snapshot analyses will be discussed and their impact on the analysis documented.

**Change #5**

**4.8 Examination of subgroups**

- Age at Visit 1 (<65 and ≥65 years).
- Time since first diagnosis of epilepsy (0-<1 years, 1-<5 years, 5-10 years, >10 years): Defined in [Section 6.2](#)
- Number of concomitant Baseline AEDs (0, 1, ≥2AEDs) : Defined in [Section 6.4](#)
- Number of Historical AEDs (0, 1, 2, ≥3): Defined in [Section 6.4](#)
- Historical Levetiracetam (LEV) use (Yes, No): Defined in [Section 6.4](#)
- 28-day Baseline all seizures frequency (≤5, >5-10, >10) : Defined in [Section 8.2.2.1](#)

**Has been changed to:**

- Age at Visit 1 (<65 and ≥65 years).
- Time since first diagnosis of epilepsy (0-<1 years, 1-<5 years, 5-10 years, >10 years): Defined in [Section 6.2](#)
- Number of AEDs at Study Entry (0, 1, ≥2AEDs) : Defined in [Section 6.4](#)
- Number of Historical AEDs (0 or 1 or 2 or 3, 4 or 5 or 6, >6): Defined in [Section 6.4](#)

- Historical Levetiracetam (LEV) use (Yes, No): Defined in [Section 6.4](#)
- Number of Lifetime AEDs (0 or 1 or 2 or 3, 4 or 5 or 6, >6): Defined in [Section 6.4](#)
- 28-day Baseline all seizures frequency ( $\leq 5$ ,  $>5-10$ ,  $>10$ ): Defined in [Section 8.2.2.1](#)

